A post-baccalaureate study coordinator with a background in psychology or a related field will perform many important tasks for the U01 project. After appropriate training, the study coordinator will conduct the bulk of the initial telephone screening interviews. He/she will also conduct diagnostic interviews at baseline and one-month and three-month follow-up assessments and track attendance at scheduled dental appointments for the 12-month period following the dental anxiety intervention. He/she will also complete reliability ratings for diagnostic interviews conducted by other study staff, providing full coverage of this activity with the graduate student. The study coordinator will also be charged with the rating of treatment fidelity/adherence of a portion of the

Page 6 of 28 Revision: May 12, 2023

interventions completed during the U01 project. The study coordinator will also conduct a range of data entry and management activities.

The dental staff for the proposed U01 will be two or more part-time dental assistants or expanded function dental assistants as defined in the State of Pennsylvania working with [name] at TUKSoD (one full-time equivalent). They will be trained in the administration of the Internet-based dental anxiety intervention by a psychologist, postdoctoral fellow, or doctoral student highly trained in CBT and the specific online intervention, and they will administer the dental anxiety intervention to those patients randomly assigned to the arm of the trial in which the intervention is delivered by dental staff. They will also assist in the payment of study subjects and other day-to-day tasks when these activities cannot be performed by the post-baccalaureate study coordinator.

7) Prior Approvals

See attached letters of support from the Directors of the Faculty Practice Clinic and the Graduate Clinics of TUKSoD.

8) Study Design

a) Recruitment Methods

Approximately 550 patients will participate in this research, roughly evenly divided between the three arms of the study.

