Pain Sensitivity Index (PSI; Gross, 1992a). The PSI is a 16-item self-report measure that assesses the fearful appraisal of pain and the expected physical, psychological, and social consequences of pain. Items are rated on a scale ranging from 0 (not at all) to 7 (very much) reflecting the degree to which the item applies to the respondent. Higher scores indicate higher levels of pain sensitivity. The scale has demonstrated high internal consistency in previous studies with dental patients (α = 0.92) (Klages et al., 2004). It was found to measure a construct distinct from dental phobia and health concerns (Gross, 1992a). Pain sensitivity is considered a stable characteristic that can influence the development of situational fears (Gross, 1992b). It has been related to dental anxiety and expectation of pain before dental procedures (Klages et al., 2004). The PSI will play a dual role in this study, as a secondary outcome measure and as a hypothesized moderator of the efficacy of the Internet-based dental anxiety intervention compared to the active control condition. It will be administered at baseline and the 1-month and 3-month follow-ups.

Distress Tolerance Scale (DTS; Simons & Gaher, 2005). The DTS is a 15-item self-report measure assessing one's perceived ability to experience and tolerate negative emotional states. This scale measures four dimensions of distress tolerance: subjective appraisal of distress, ability to tolerate emotional distress, absorption of attention by negative emotions, and regulation efforts to alleviate distress. Items are rated on a scale ranging from 1 (strongly agree) to 5 (strongly disagree). Total score range from 15 to 75, with higher scores reflecting higher levels of distress tolerance. This scale has high internal consistency (α = .89), appropriate convergence with other self-report ratings of affective distress and regulation, and adequate six-month test-retest reliability (r =.61). The DTS will also play a dual role in this study, as a secondary outcome measure and as a hypothesized moderator of the efficacy of the Internet-based dental anxiety intervention compared to the active control condition. It will be administered at baseline and the 1-month and 3-month follow-ups.

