injury-injection phobia). Statistical significance will be set at p < .05. MI will be used to handle missing follow-up data as described below.

Specific Aim 3

Aim 3 examines the impact of the intervention on attendance at scheduled dental appointments over the following 12-month period to determine whether the intervention affects avoidance of dental procedures. First, we will examine whether the overall attendance rate is changed from pre- to post-intervention using a one-sample Chisquare test comparing the 12-month periods immediately before and immediately after the delivery of the intervention. The two intervention groups combined will be used for this analysis. We will also use a Chi-square test to compare post-intervention attendance rates between the two intervention groups. We expect the attendance rates will be similar for the two groups. Finally, we will conduct logistic regression analyses predicting attendance/nonattendance among intervention patients who did or did not demonstrate reduction in dental anxiety at 3-month follow-up. Relevant demographic characteristics and other potential confounding variables or moderators will be included in the final logistic models.

Missing Data

MI will be used to handle missing follow-up data when conducting ITT analysis for Specific Aims 1 and 2. There will be three steps in the MI procedure: 1) The missing follow-up data will be filled in 100 times to generate 100 complete datasets; 2) The 100 datasets will be analyzed by analyses of covariance with follow up scores at 1-month or 3-month as outcomes and treatment groups as the independent variable (Tr1 vs. Tr2 for Specific Aim 1, or Tr1 + Tr2 vs. AC for Specific Aim 2), controlling for baseline scores; 3) The results from the 100 complete datasets will be combined for the MI inference (Rubin 1987). SAS PROC MI and PROC MIANALYZE will be used for multiple imputation analysis using SAS 9.4 (SAS Institute Inc., Cary, NC, USA).

Analysis of Secondary Objectives

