To determine whether primary objectives 1 and 2 are reflected in measures of other related constructs such as pain sensitivity, distress tolerance, anxiety sensitivity, and anticipated and perceived pain and anxiety, the statistical methods described above will be used. The moderating role of distress tolerance and pain sensitivity as expressed in the secondary objectives will be assessed as well. We will examine whether baseline levels of distress tolerance and pain sensitivity moderate the efficacy of the dental anxiety intervention. We will examine the moderating effect of these factors on the intervention and the reduction in dental anxiety at the 1-month and 3-month follow-ups. For moderation analyses, we will include a dummy variable for randomization arm, the potential moderator variable (distress tolerance or pain sensitivity), and an interaction term between the two (i.e. dummy variable multiplied by the mean-centered moderator variable). To maintain power to detect moderation, we will explore moderators

Page 18 of 28 Revision: May 12, 2023

separately. We will also use linear-mixed effects models in which we include potential confounding variables, as well as main effects and interaction terms of interest.

d) Withdrawal of Subjects

We do not expect that there will be much in the way of withdrawal during the dental anxiety intervention itself, although it is not entirely out of the realm of possibility. We expect that the major concerns will have to do with the assessments over time, and in that case, concerns over withdrawal are really concerns over retention. However, we note a few issues below.

Reasons for Withdrawal related to the Intervention

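### The stated moderation model leaves out the baseline anxiety score: this costs precision and, if baseline anxiety modifies the I-CBT effect, cannot tell the two moderators apart from it

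*Combined protocol and SAP*

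**What the plan says.** The objective is stated as "We will examine whether baseline levels of distress tolerance and pain sensitivity moderate the efficacy of the dental anxiety intervention". The descriptions of the Pain Sensitivity Index (PSI) and the Distress Tolerance Scale (DTS) each call the scale a "hypothesized moderator of the efficacy of the Internet-based dental anxiety intervention compared to the active control condition". The contrast is therefore I-CBT against control.

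The Analysis of Secondary Objectives gives a concrete model, fitted to one moderator at a time: "we will include a dummy variable for randomization arm, the potential moderator variable (distress tolerance or pain sensitivity), and an interaction term". The target is improvement in dental anxiety at one and three months. The dependent variable (change score or follow-up score) is not defined. The same paragraph then adds: "We will also use linear-mixed effects models in which we include potential confounding variables, as well as main effects and interaction terms of interest". Neither the confounders nor the interaction terms are named.

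Elsewhere the plan does use the baseline score. Under Missing Data, the imputed-data analyses for Aims 1 and 2 are analyses of covariance of the follow-up score, adjusted for baseline. On pain sensitivity the PSI description says: "It has been related to dental anxiety and expectation of pain before dental procedures". It also calls the scale distinct from dental phobia. No correlation is given, and no link between distress tolerance and dental anxiety is stated.

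**The concern.** The baseline score of the outcome is usually the strongest predictor of the follow-up score, and it is already collected. Leaving it out of the only moderation model that is written out enlarges the error of an interaction test.

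The second issue is interpretation. Patients who start higher on a scale with a floor have more room to improve, so baseline anxiety may itself modify the I-CBT effect. If it does, and the moderator is correlated with baseline anxiety, the arm x moderator term absorbs part of that modification. A stated secondary objective could then be reported as moderation by pain sensitivity in its own right when starting severity explains it.

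**Working it through.** The plan gives no power or error-rate figure for moderation, so there is nothing of its own to reproduce.

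**Inputs from the protocol.** Sample: "Approximately 550 patients will participate in this research, roughly evenly divided between the three arms of the study" (section 8(a)). With the two I-CBT arms pooled this is about 367 against 183. Test level: "Statistical significance will be set at p < .05" (Specific Aim 2), taken as two-sided for moderation, where no level is given. The MDAS total runs from 5 to 25.

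**Assumptions, not in the documents.** Baseline/follow-up correlation r = .6; equal SDs; moderator/baseline correlation ρ = .3 to .5; I-CBT benefit growing by k = .2 to .4 SD per SD of baseline anxiety; no effect of the moderator itself. For scale, a 3-point benefit at MDAS 18 that is proportional to the distance above the floor gives k = 3/(18 − 5) = .23.

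**1. Precision (k = 0).** Residual variance of the stated model:
- Change score as outcome: (1 − r)²(1 − ρ²) + (1 − r²). At ρ = .3 this is .16 × .91 + .64 = .786; at ρ = .5 it is .16 × .75 + .64 = .760.
- Follow-up score as outcome: r²(1 − ρ²) + (1 − r²). At ρ = 0 this is 1.00; at ρ = .3, .968; at ρ = .5, .910.

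With the baseline score added it is 1 − r² = .64 in all cases. The SE ratios are √(.64/.786) = .90 and √(.64/.760) = .92 for the change score, and .80, .81 and .84 for the follow-up score. The gain is therefore about 8% to 20%.

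**2. What the interaction picks up.** The mean of baseline anxiety given the moderator is ρ times the moderator (both in SD units). Without an arm x baseline term, the arm x moderator coefficient has expected size k × ρ:
- .2 × .3 = .06
- .3 × .4 = .12
- .4 × .5 = .20

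The simulated SE at k = 0 is about .08. If k = 0 the coefficient is zero whatever ρ is. Because arm is randomised, adding baseline as a main effect leaves k × ρ unchanged and only shrinks the error.

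**3. Rejection rate for a moderator with no effect of its own** (change-score outcome in the stated model, 183 against 367, two sets of 2,000 simulated trials per setting except where one range is shown):

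| ρ, k | Stated model | + baseline | + baseline and arm x baseline |
|---|---|---|---|
| .3, .2 | 9.4%, 10% | 12.6%, 14% | 4.8%, 5% |
| .4, .3 | 27%, 25% | 37%, 37% | 4.6%, 5% |
| .5, .4 | 60%, 59% | 77%, 77% | 5.1%, 5% |
| .3 to .5, .23 | 11% to 26% | 15% to 35% | 4% to 5% |
| any ρ tried, 0 | 5% to 6% | 5% to 6% | 5% to 6% |

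A separate simulation used the follow-up score as outcome, a baseline slope of .5 and 3,000 trials per setting. At N = 550 the stated model rejected in 4.6% to 5.9% of trials at k = 0 for ρ from 0 to .5. At k = .15 it rejected in 7%, 8% and 15% (ρ = .2, .3, .5), and at k = .3 in 11%, 20% and 43%. Baseline as a main effect changed the last figure to 45%. Adding arm x baseline brought every setting to 4% to 6%.

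**4. Price of the arm x baseline term (k = 0, against the stated change-score model).** The variance becomes (1 − r²)/(1 − ρ²). At ρ = .5 this is .64/.75 = .853, and √(.853/.760) = 1.06, so the SE is 6% larger (simulated .0792 to .0842). At ρ = .3 it is .64/.91 = .703, and √(.703/.786) = .95, so the SE is 5% smaller (simulated .0807 to .0765).

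**The case against.** Four arguments on the other side carry weight.

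- **The mixed-model sentence.** It promises confounders and interaction terms. A reader might infer that confounders enter as main effects only, but the text does not say so. Baseline score and arm x baseline could be among the unnamed terms. This stands as far as it goes: they are neither excluded nor required, and the plan does not say which model decides if the two disagree.
- **Correlation alone does no harm.** A reader might infer that a variable that merely tracks baseline anxiety will be declared a moderator. The documents do not support that. The 5% error rate holds unless baseline anxiety modifies the treatment effect, and no such modification is reported. Even where it is assumed, most settings give rates well below 50%. Enrolment is also restricted to high MDAS scores, which would tend to narrow the baseline spread and weaken both assumed quantities.
- **Marginal moderation is a legitimate target.** The objective does not say independently of baseline anxiety. If benefit differs by pain sensitivity because severity differs, that is still a true and predictive difference. This stands, and it rules out treating the adjusted term as the only valid answer.
- **Evidence for one moderator only.** The documented link is for pain sensitivity. For distress tolerance the mechanism is an open possibility.

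The precision argument survives all four. Its size depends on the undefined outcome variable and on the assumed r.

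**Conclusion.** The point holds in a limited form. The moderation model that the protocol writes out omits the baseline score of the outcome, and the further models do not name that score or its product with arm. The loss of precision is about 8% to 20% of the interaction's standard error if r = .6. The ambiguity of interpretation is conditional. Over the assumed range the chance of an apparent moderator with no effect of its own is about 10% to 60%, about 12% to 26% at the floor-based value of .23, and about 5% if baseline anxiety does not modify the effect. All these rates rest on correlations and modification sizes that the documents do not give. No primary conclusion is affected; this is a secondary objective that is cheap to make interpretable.

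**What to change.** In the Analysis of Secondary Objectives, state for each moderator separately:

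1. Model A: follow-up score at 1 or 3 months on arm, moderator, arm x moderator, and the baseline score of the same outcome (MDAS or ADIS-5 fear). This answers whether benefit differs by level of the moderator, with better precision than the stated model.
2. Model B: Model A plus arm x baseline score. Report its arm x moderator term beside that of Model A.
3. Wording rule: describe a moderator as independent of baseline anxiety only if its interaction holds in Model B. Otherwise report it as a difference in benefit that baseline severity may explain.

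Model A alone does not settle the second question, because a baseline main effect does not remove the shared modification (about 13% to 77% in the simulations).

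The cost is two extra terms and no new data. Under the same assumptions, the interaction's standard error in Model B is up to about 6% larger than in the stated model when ρ = .5 and baseline anxiety does not modify the effect. At ρ = .3 it is about 5% smaller.

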individualized treatment as needed. During this time, to the extent that clinical circumstances allow, he/she will attempt to ascertain whether specific portions of the intervention contributed to the patient's distress (that is, to the extent possible, he/she will attempt to conduct the post-intervention debriefing interview or gather as much of that type of information as the patient will tolerate). [name] or [name] will be available by cell phone to consult as needed in this process.

For the second reason (failure to attend the following dental appointment), the patient will be withdrawn from study consideration unless the dental appointment can be rescheduled within 72 hours. We will attempt to help patients do so, because it is likely that they would still benefit from the dental anxiety intervention if the dental appointment can be rescheduled more or less immediately; research staff will interact with dental clinic staff to facilitate this as much as possible.

For the third reason (failure to attend the dental anxiety intervention), the patient will be withdrawn after reasonable attempts to reschedule have failed or if there is a rescheduled appointment and the patient fails to appear.

For the fourth reason (failure to complete assessments), the circumstances will be different depending on the timing of the problematic assessment. If the patient does not complete the pre-intervention assessments, the intervention will not be delivered, and thus the patient will be effectively withdrawn. The patient will be called no less than 3 times to facilitate such completion, but a number of patients may not complete because of this issue. They will be replaced so that we reach our enrollment target. If the patient fails to complete assessments at follow-up, no less than 3 calls will be made, but the patient will be considered lost to follow-up rather than withdrawn. In our recent randomized trial (Tellez et al., 2015), which included only a one-month follow-up, only 2 of 46 intervention patients were lost to follow-up in this way.

e) Privacy & Confidentiality

As in any type of treatment or clinical research program, patients' privacy must be carefully guarded and respected. All identifying information (e.g., contact information) and audio recordings of interviews or video recordings of the I-CBT session will be stored in locked files or digitally on a HIPAA-compliant network. Remaining data will be stored in password-protected computer files on a HIPAA-compliant network. One file will contain patient names, contact information, and associated subject codes; at the end of the study, this file will be destroyed. All other data will reside in a file identified by subject codes and from which other identifying information will have been removed, so the link between these data and subject identifiers will have been severed.

All assistants and others working on the project will be educated about the importance of strictly respecting patients' rights to confidentiality and will have completed training concerning proper practice in accordance with HIPAA regulations.

Page 20 of 28 Revision: May 12, 2023

Data files will be accessible only to the investigators, study coordinator, postdoctoral fellow, doctoral student, and research assistants directly connected with the study. Only members of the research team will review the data. To help patients feel at ease, the study coordinator and other staff will emphasize their right to ask questions throughout the study and to abstain from any aspect of the research which makes them uncomfortable.

No data will be shared with persons unassociated with the project without prior written release from the patient. When the results of this protocol are published, no participant will be identified by name.

This research is covered by a Certificate of Confidentiality from the National Institutes of Health. A Certificate of Confidentiality helps protect identifiable information and biological samples. The researchers with this Certificate may not disclose or use information, documents, or biospecimens that may identify participants in any federal, state, or local civil, criminal, administrative, legislative, or other action, suit, or proceeding, or be used as evidence, for example, if there is a court subpoena, unless a participant has consented for this use. Information, documents, or biospecimens protected by this Certificate cannot be disclosed to anyone else who is not connected with the research except, if there is a federal, state, or local law that requires disclosure (such as to report child abuse or communicable diseases but not for federal, state, or local civil, criminal, administrative, legislative, or other proceedings, see below); if a participant has consented to the disclosure, including medical treatment; or if it is used for other scientific research, as allowed by federal regulations protecting research subjects.

The Certificate cannot be used to refuse a request for information from personnel of the United States federal or state government agency sponsoring the project that is needed for auditing or program evaluation by the National Institute of Dental and Craniofacial Research (NIDCR) which is funding this project or for information that must be disclosed in order to meet the requirements of the federal Food and Drug Administration (FDA). Participants should understand that a Certificate of Confidentiality does not prevent the voluntary release of information about themselves or their involvement in this research. If a participant wants their research information released to an insurer, medical care provider, or any other person not connected with the research, they must provide consent to allow the researchers to release it.

The Certificate of Confidentiality will not be used to prevent disclosure as required by federal, state, or local law of child abuse and neglect, or harm to self or others. The Certificate of Confidentiality will not be used to prevent disclosure for any purpose a participant has consented to in this informed consent document (their baseline dental anxiety score will be reported to the dentist prior to the scheduled dental appointment).

9) Risks to Subjects

Page 21 of 28 Revision: May 12, 2023

Risks Associated with Intervention Procedures:

Internet-based dental anxiety treatment intervention: Based on our experience with the computer-based version of this intervention and our pilot of the online version as part of the R34 project, there are few significant risks. It is certainly possible, and will undoubtedly be the case for a subset of the sample, that the patient could experience elevated anxiety while interacting with the intervention materials, as these involve exposure to descriptions or videos of dental procedures selected specifically because they induce anxiety or are avoided in real life. In our earlier acceptability trial of the computer-based version, some patients did note elevations of anxiety and accompanying physiological symptoms, and some reported annoyance about it, but none asked to stop the intervention midway, and none chose to cancel their immediately following appointments for dental treatment. This experience was replicated in the randomized controlled trial and the piloting that occurred as part of the R34 grant.

Active Control Condition: This comparison condition will have patients pursue their scheduled dental appointment as usual, with the exception that their score on their most recent administration of the MDAS, the measure of dental anxiety, would be shared with the dental care provider (also the case in the intervention conditions). In addition, control participants will be asked to view a video of nature scenes for a period of time equivalent to the dental anxiety intervention. We cannot foresee any significant risks associated with these procedures.

Recording: Some patients may feel uncomfortable about the treatment sessions being recorded for the assessment of treatment fidelity, but this will be a required procedure. Treatment fidelity ratings as well as informal observations of session video-recordings by the study coordinator will be used for feedback to dental assistants undergoing training. Debriefing interviews, which will be audio-recorded, will provide additional important information about modifications that may need to be made to the dental anxiety intervention in advance of further research on the treatment of dental anxiety.

Risks Associated with Assessment Procedures:

Self Report Measures and Assessor Ratings: No risks are seen associated with these assessment procedures other than discomfort associated with thinking about one's dental anxiety as well as the recording of assessor interviews involving the disclosure of personal information. Recording will be necessary for the measurement of inter-rater agreement on interview measures.

Protection Against Risk:

1. Careful screening to identify patients whose risk for potential adverse outcomes is elevated were they to participate in the proposed research. Such patients will be excluded from the study. As an example, an actively suicidal patient would be excluded from study participation and appropriate clinical treatment provided.

Page 22 of 28 Revision: May 12, 2023

- 2. Clinical staff will be trained to cope with any anxiety experienced by specific patients during treatment sessions. Here we refer to psychology staff who have experience in the treatment of anxious patients, at least one of whom will be on site (or available by cell phone) at all times to provide support for any patient who is unusually troubled by the experiences of the intervention. As a further safeguard, we have added a section to both the didactic portion of the training for therapy aides (both psychology staff and dental assistants) and the accompanying manual on the identification of and intervention with extreme anxiety reactions that may occur as a result of exposure to the intervention materials. As noted above, we see this risk as quite small, but not impossible.
- 3. Continuing contact with patients during the follow-up period. Patients will have contact with the same assessors at follow-up assessments as they did at baseline whenever possible. Patients will be encouraged to make contact with project staff between contacts if their dental anxiety or any reaction to the intervention causes undue distress. In that case, a discussion will be engaged about whether or not the patient should be withdrawn from the follow-up phase of the study and given appropriate clinical care. That care may take any of a variety of forms and may be offered through the Psychological Services Center of Temple University or through appropriate referral, depending on resources and the type of treatment desired by the patient.
- 4. As in any type of treatment or clinical research program, patients' confidentiality must be carefully guarded and respected. All data with identifying information will be stored in locked files or password-protected computer files. Data being analyzed will be identified by subject codes, and identifying information will be removed. All assistants and others working on the project will be educated about the importance of strictly respecting patients' rights to confidentiality and will have completed training concerning proper practice in accordance with HIPAA regulations.
- 5. In addition to the investigators' responsibility for oversight, study oversight will be under the direction of the NIDCR Medical Monitor. The investigators will submit a report every 6 months to the NIDCR Medical Monitor for review. This report will include data regarding enrollment and retention, unanticipated problems and protocol deviations, outcome measures, quality management findings and other relevant parameters. The IRB and the designated program person at NIDCR will be notified in writing by [name] or [name] if a serious adverse event occurs. A serious adverse event is defined as follows: death, life-threatening adverse event, inpatient hospitalization or prolongation of existing hospitalization, persistent or significant disability/incapacity, congenital anomaly/birth defect, and medically significant event. Risks of participation will be continuously monitored and appropriate measures implemented in cases of unforeseen adverse events. These events will be reported whether or not they appear to be related to study procedures.

All protocol violations will be discussed in detail; if appropriate, the IRB will be consulted and corrective actions devised. All modifications to the protocol will be submitted for IRB

Page 23 of 28 Revision: May 12, 2023

approval. Summaries of all relevant discussions will be promptly disseminated to study personnel via e-mail and retraining procedures implemented as needed.

10) Potential Benefits to Subjects

An earlier iteration of the dental anxiety intervention demonstrated efficacy in the treatment of dental anxiety in the same population of patients from which the current sample will be drawn. Therefore, it is possible that a portion of the patients in this study will realize a reduction in their own dental anxiety, although this cannot be assured for any specific patient. Patients will receive a thorough assessment of their dental anxiety, and the intervention includes substantial educational material about dental anxiety, which should be to their benefit, regardless of anxiety reduction. Patients will be offered referrals for further treatment of dental anxiety, through the Temple University Psychological Services Center or elsewhere, should they be interested in pursuing this.

11) Costs to Subjects

Dental anxiety intervention is provided without charge. The investigators are not involved in the determination of cost of actual dental procedures, but no additional dental procedures will be conducted in the course of this research.

12) Informed Consent

The protocol will follow INVESTIGATOR GUIDANCE: Informed Consent (HRP-802) to obtain informed consent from participants. The proposed sequence is described as part of the narrative to follow. Although we have been thorough in delineating possible risks to participants, our experience with the prior computer-based version of the dental anxiety intervention suggests that this is truly a minimal risk study. However, we understand that that determination is ultimately one for the IRB rather than the investigators.

Informed consent is a process that is initiated prior to the individual agreeing to participate in the study and continues throughout study participation. Extensive discussion of risks and possible benefits of study participation will be provided to patients during the screening contact (Time 0) and electronic informed consent will be obtained at the first in-person visit (Time 2). Copies of the signed primary consent form will be emailed to patients for their records at the first Clinic Visit. The rights and welfare of the patients will be protected by emphasizing to them that the quality of their clinical care will not be adversely affected if they decline to participate in this study. Patients may withdraw consent at any time over the course of the study.

The consent process will be documented in the clinical or research record.

Participants in this study will be patients who have scheduled appointments for nonemergent dental procedures through the Faculty Practice Clinic at TUKSoD (and the Graduate Clinics of TUKSoD, if necessary). All such persons will be contacted by

Page 24 of 28 Revision: May 12, 2023

telephone and asked if they would be willing to be screened for dental anxiety and, if so, if they would be interested in the possibility of participating in a study of the treatment of dental anxiety. If the potential participant gives a positive response, the 5-item dental anxiety screening measure, two additional screening questions (age, impairment as a result of dental anxiety), and a medical screening interview will be administered (see Recruitment Methods section for a more detailed presentation of specific procedures). If the participant meets criteria and continues to express interest in the study, extensive information about the study and the risks and possible benefits of study participation will be provided (the caller will provide a full summary of the primary study consent form over the telephone with the potential participant and verbal consent for full study participation will be obtained). If patients remain interested in participation, they will be scheduled for a second ("baseline") interview and questionnaire administration.

At the Clinic Visit on the day of the dental anxiety intervention (or control session), the primary study consent form will be reviewed with the patient and remaining questions answered. A copy of this signed consent form will be provided to the patient via email, but a physical copy can also be provided upon request. As part of the overall consent procedure, patients will be informed of the nature of the investigation, the types of assessments and treatments involved, the recording of debriefing/assessment interviews and intervention sessions, alternative treatments, and the potential risks involved in participation. In addition, an explanation of how information related to their case will be handled will be presented. The IRB will have approved the protocol and consent form prior to implementation.

13) Vulnerable Populations

Not applicable. Individuals who are vulnerable to coercion or undue influence will not be included in the human subjects activities described herein.

14) References

